8.2.2. Modification of the clinical decision in CPT for each sub-group

Calculation of the net reclassification index (NRI):

$$NRI (\%) = (P_{upevents} - P_{downevents}) - (P_{upnonevents} - P_{downnonevents})$$

- For the subpopulation with a CT-scan < 12h;
- For each clinical hypotheses ;
- For the level of certainty of clinical hypotheses:
 - o Likert scale: strongly certain, certain, neither certain nor uncertain, uncertain, strongly uncertain;
- For each type of patient (reason for hospitalization the most represented);
- For each research center.

8.2.3. Agreement between clinical and LUS diagnosis

Calculation of Kappa index:

The clinical diagnosis and the lung ultrasound allow to diagnose the following events : (the retained airway secretions and bronchospasm diagnoses aren't included in the analysis as LUS doesn't allow their diagnosis (LUS may only be compatible with these hypotheses):

- T1: pneumonia/consolidation;
- T2: atelectasis (~~passive or active mechanism~~ obstructive);
- T3: pleural effusion;
- T4: pulmonary edema or global interstitial syndrome;
- T5: pneumothorax;
- T6: reduced aeration at the most dependent parts of the lungs;
- T7: diaphragm dysfunction (unilateral or bilateral);
- T8: examination is inconclusive.

Contingency table:

		Lung ultrasound								Total
		T1	T2	T3	T4	T5	T6	T7	T8	
Clinical diagnosis	T1									
	T2									
	T3									
	T4									
	T5									
	T6									
	T7									
	T8									
Total										

Proportion of observed agreement:

$$P_a = \frac{1}{n} \sum_{i=1}^p n_{ii}$$

Theoretical proportion of observed agreement:

$$P_e = \frac{1}{n^2} \sum_{i=1}^p n_{i.} \cdot n_{.i}$$

Kappa :

$$\kappa = \frac{P_a - P_e}{1 - P_e}$$

The Kappa index will be calculated for the global population, the population where the clinical diagnosis is « strongly certain/certain » and « strongly uncertain/uncertain » and the population with a CT-scan < 12h.

8.2.4. Proportion of cases when the chest physiotherapy protocol is modified following the results of the LUS:

Calculation of proportion: $P_{\text{upevents}} + P_{\text{upnonevents}}$ for all of the clinical hypothesis, for each clinical hypothesis and in the CT-scan <12h subpopulation.

With a confidence interval at $\alpha=0.05$.

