The basics lung ultrasound semiology is described in annexe 3b. The following syndromes will be searched for: normal profile, alveolar-interstitial syndrome, pulmonary consolidation, pleural effusion, pneumothorax and diaphragm dysfunction (16).

The ultrasound syndromes are defined by the following signs in a scanned for the in six-lung zones of each chest wall of the patient:

Normal lung:

- Bat sign;
- A lines;
- Pleural sliding (seashore sign).

A normal profile is compatible with presence of tracheo-bronchial retained secretions and bronchospasm.

Alveolar-interstitial syndrome(16–18):

- A positive region is defined by the presence of three or more B-lines in a longitudinal plane between two ribs;
- In the anterior and lateral thoracic areas;
- Multiple and well-defined B-lines: moderate loss of lung aeration;
- Confluent B-lines: severe loss of lung aeration.

The presence of a focal sonographic pattern of interstitial syndrome is compatible with pneumonia, atelectasis or pulmonary contusion.

The presence of multiple diffuse bilateral B-lines is compatible with pulmonary oedema or ARDS. In the case of pulmonary oedema, the interstitial syndrome is diffuse, homogeneous and bilateral. In the case of ARDS, the interstitial syndrome is diffuse, heterogeneous, bilateral and associated with pleural abnormalities and sub-pleural consolidations.

Lung consolidation:

- Subpleural echo-poor region or tissue-like echo-structure;
- Atelectasis pattern(19,20):

- Abolished pleural sliding;
 - Static air bronchogram;
 - Lung pulse;
 - Passive atelectasis due to compression from the surrounding pleural effusion: homogeneous echogenic structure into the pleural effusion, with smooth margin and linear air bronchogram(21).
- Pneumonia pattern(22–25):
- Irregular deep margin when the consolidation is partial;
 - Regular deep margin when consolidation involves an entire lobe;
 - Static or dynamic air bronchogram;
 - Fluid bronchogram;
 - Vascular pattern;
 - Bilateral or unilateral.

The aim of physiotherapist is not to identify the medical diagnosis. Regarding the presence of the interstitial syndrome and lung consolidation, the aim is to also define the level of lung aeration present in each of the 12 lung zones:

- Normal aeration (N): presence of lung sliding with A-lines or fewer than two isolated B-lines;
- Moderate loss of lung aeration (B1): multiple, well-defined B-lines (B1 lines);

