7.4.3. Initial clinical physiotherapist visit

The clinical physiotherapist undertakes the patient clinical examination, reviews the chest x-rays and additional tests as available. Moreover, he/she reviews the CT-scan if performed < 12h at the patient's admission including the radiology report. Following the clinical examination, the clinical physiotherapist formulates his/her clinical hypotheses. Among this formulated clinical hypotheses, the physiotherapist chooses a primary clinical hypotheses (the choice is left to the discretion of the clinical physiotherapist, based on the probability and priority of the clinical hypothesis in term of treatment). The primary clinical hypothesis and the secondary clinical hypotheses (if adapted) will be recorded in the case report form (CRF). According the primary clinical hypothesis, the clinical physiotherapist records his chest physiotherapy treatment modalities in the CRF.

The following data will be recorded:

- Medical management:
 - o Hypnotics ~~(and dose)~~;
 - o Opiates ~~(and dose)~~;
 - o Steroids ~~(and dose)~~;
 - o Anti-hypertensives ~~(and dose)~~;
 - o Antibiotics ~~(and dose)~~;
 - o Oxygen therapy (and flow);
 - o Mechanical ventilation, NIV (PEEP, IPAP, O₂ dose);
 - o Tracheotomy;
- Severity score: SAPSOFA
- Vital signs: RR, HR, BP SpO₂, FiO₂ (true or estimated), body temperature, RASS, Glasgow coma score;
- Clinical hypotheses of the clinical physiotherapist;
- Choice of chest physiotherapy protocol (before LUS).

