7.4.4. Ultrasound physiotherapist/operator visit

Following the clinical physiotherapist visit, the ultrasound physiotherapist/operator performs a lung and diaphragm ultrasound. He is blinded to the patient's status and clinical physiotherapist examination. He/she is not involved in patient management or patient clinical decision-making. The ultrasound findings are recorded in the LUS report (*cfannexe4*). The LUS report is reported to the clinical physiotherapist and to the intensivist. The ultrasound diagnosis(es) is recorded.

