P = pleural line; Rs = superiorrib; Ri = inferiorrib; Pp = parietal pleura; Pv = visceral pleura; Pe = pleural effusion; C =lung consolidation; D = diaphragm; Br = air bronchogram.

Annexe 4: Lung and diaphragm ultrasound scan report

VENTILATOR SETTINGS (Surround the mode and fill the settings at the moment of LUS examination)						
Mode	ACV	SIMV	PCV	PSV	NIV	Spontaneously Breathing
Settings	Tidal volume =		PEEP =	PS =	PEEP =	

PNEUMOTHORAX				
Right	Present	Absent	Left	Absent
If present, locate the lung point in the diagram below (place an « X »)				

LUNG AERATION					
	LAT	ANT	ANT	LAT	
POST					POST
Superior	Pleural sliding Lung pulse	Pleural sliding Lung pulse	Pleural sliding Lung pulse	Pleural sliding Lung pulse	Pleural sliding Lung pulse
Inferior	Pleural sliding Lung pulse	Pleural sliding Lung pulse	Pleural sliding Lung pulse	Pleural sliding Lung pulse	Pleural sliding Lung pulse
Indicate level of lung aeration (0, 1, 2, 3) in the above diagram			LUS score = /36		
When lung consolidation is present, indicate the appropriate letter(s) (in the above diagram, following the « 3 ») :					
a. Deep limit with Shred sign		d. Static air bronchogram		g. Fluid bronchogram	
b. Deep limit well defined		e. Punctiform air bronchogram		h. Vascular pattern	
c. Dynamic air bronchogram		f. Linear air bronchogram			

PLEURAL EFFUSION								
	Right				Left			
PLD (cm)								
Pattern	Anechoic	Heterogeneously echogenic	Homogeneously echogenic	Septated	Anechoic	Heterogeneously echogenic	Homogeneously echogenic	Septated

DIAPHRAGM				
	Right		Left	
tdi/tde (cm)				
DTF (%)				
EXC (cm)				

ULTRASOUND DIAGNOSTIC				Scan quality:
Normal		Pneumothorax (L), (R) or Both		
Alveolar-interstitial syndrome		Focal	Diffuse	Good
		Homogeneous	Heterogeneous	
Lung consolidation		Moderate	Severe	Poor
		Atelectasis pattern		
Pneumonia pattern		Atelectasis pattern		Sonographer:
Unilateral (L) or (R)	Bilateral	Obstructive	Passive	
Pleural effusion		Unilateral (L) or (R)	Bilateral	
		Transudative pattern	Exsudative pattern	
Diaphragm dysfunction		Loss of aeration in the most dependent parts of the lungs		
Unilateral (L) or (R)	Bilateral	No conclusion

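### The single 8×8 kappa in section 8.2.3 needs one ultrasound diagnosis per patient, but a scan may return several and no rule selects one

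*Combined protocol and SAP*

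**What the plan says.** **The table.** Section 8.2.3 introduces its categories with "The clinical diagnosis and the lung ultrasound allow to diagnose the following events" and puts the same eight on both axes, T1 to T7 for conditions and "T8: examination is inconclusive" as the last. Retained secretions and bronchospasm are left out. Observed agreement is the diagonal count over n, and expected agreement is the sum of the products of the margins over n². Kappa is planned for the whole population, for two certainty groups and for patients with a recent CT scan. The section does not define the unit counted by n, or say which diagnosis is entered when there is more than one.

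**Clinical axis.** Sections 6.5.1.4 and 7.4.3 have the physiotherapist choose one primary hypothesis and record any secondary ones. Section 8.2.3 does not say that the primary one is the row entry.

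**LUS axis.** Section 7.4.4 says "The ultrasound diagnosis(es) is recorded". Annexe 4 reports pneumothorax, aeration and consolidation, effusion, and diaphragm in separate blocks. It ends with a list of diagnoses, none marked as primary.

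**Normal and focal patterns.** Section 6.5.2.3 states: "The following syndromes will be searched for: normal profile, alveolar-interstitial syndrome, pulmonary consolidation, pleural effusion, pneumothorax and diaphragm dysfunction". Annexe 4 has an entry for a normal scan, separate from "No conclusion". Section 6.5.2.3 also says: "The presence of a focal sonographic pattern of interstitial syndrome is compatible with pneumonia, atelectasis or pulmonary contusion". In 8.2.3, T4 names pulmonary edema or a global interstitial syndrome only.

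**The concern.** Cohen's kappa is defined only when each unit has one row and one column. A patient with two LUS diagnoses has two candidate columns, and the choice changes both the diagonal and the column totals. Two analysts who both follow 8.2.3 could therefore report different kappas from the same data.

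The most natural informal rule, entering the matching diagnosis whenever there is one, is not neutral. It lets the clinical hypothesis choose the LUS code, although section 6.5.2.1 blinds the operator to the clinical evaluation.

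At stake is secondary objective 2 in section 3.2. Section 8.2.3 is the only part of section 8 that analyses it.

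**Working it through.** The plan gives no expected kappa or precision, so there is no figure to reproduce.

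**Inputs.** From the documents: the 8.2.3 formulas, kappa = (Pa − Pe)/(1 − Pe), and n = 150 (section 8.1). Assumed: eight equally frequent categories; 60% agreement; a share m of patients with one matching and one other LUS diagnosis; a share w of normal scans.

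**1. Reference case.** Pa = 0.60. Pe = 8 × (1/8)² = 0.125. Kappa = 0.475/0.875 = 0.543. The large-sample SE is √(0.60 × 0.40/150)/0.875 = 0.0457, so the 95% half-width is 1.96 × 0.0457 = 0.090.

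**2. Several diagnoses.** With equal row margins, Pe stays 0.125 whichever columns are used. Under a fixed order (for example, lowest T number first), with the other diagnosis equally likely to be any of the remaining seven, the match is entered half the time. Then Pa = 0.60 − m/2. Always entering the non-match gives Pa = 0.60 − m.

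| m | Match entered | Fixed order: Pa, kappa | Always non-match (bound): Pa, kappa |
|---|---|---|---|
| 5% | 0.543 | 0.575, 0.514 | 0.55, 0.486 |
| 10% | 0.543 | 0.55, 0.486 | 0.50, 0.429 |
| 20% | 0.543 | 0.50, 0.429 | 0.40, 0.314 |

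The shift between match-first and fixed order is m/(2 × 0.875) = m/1.75. It reaches 0.090 at m = 1.75 × 0.090 = 0.157, about 16% of patients. If the exclusion of secretions and bronchospasm left 120 patients (assumed), the SE would be 0.0511, the half-width 0.100 and the crossing point 1.75 × 0.100 = 17.5%.

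**3. Bias of match-first.** Suppose LUS is unrelated to the clinical hypothesis and a share s of scans carries two distinct diagnoses. Then Pa = (1 + s)/8 and kappa = (s/8)/0.875 = s/7. For s = 20, 50 and 100% this is 0.03, 0.07 and 0.14, where the true value is 0.

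**4. Normal scans.** In a ninth column, Pa = 0.60(1 − w) and Pe = 0.125(1 − w). Coded T8, Pa = 0.60(1 − w) + w/8 and Pe = 0.125. Dropped, kappa stays 0.543.

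| w | Own column | Coded T8 | Dropped |
|---|---|---|---|
| 2% | 0.530 | 0.532 | 0.543 |
| 5% | 0.512 | 0.516 | 0.543 |
| 10% | 0.482 | 0.489 | 0.543 |

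The two ways of keeping them differ by less than 0.01. Only dropping them matters, and it raises kappa.

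**5. Focal interstitial pattern.** The documents give no frequency, so no size is attached to this gap.

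**The case against.** The strongest reply is that section 6.5.1.4 already has the physiotherapist judge whether the scan is compatible with the hypotheses. That stands as far as it goes: a raw proportion of agreement (section 4.2, item 2) could be taken from it. It does not yield kappa. When the answer is no and the scan has several findings, the column is still unknown, so the column totals and Pe are undefined.

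It is also fair to say that this is one secondary statistic in a self-described pilot study. That limits the weight of the point.

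Four stronger readings are tempting, and the documents do not support them:

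- **That the ARDS description proves double coding.** The text reads: "In the case of ARDS, the interstitial syndrome is diffuse, heterogeneous, bilateral and associated with pleural abnormalities and sub-pleural consolidations". It could mean T4 plus T1, but it equally describes one pattern, for which Annexe 4 offers diffuse and heterogeneous boxes under interstitial syndrome. It can be coded T4 alone. Passive atelectasis with effusion is similarly arguable, since Annexe 2b groups the two. Firmer support is the block structure of Annexe 4 and the separate diaphragm examination in Annexe 3a: T7 can accompany any lung finding.
- **That the coding choice outweighs sampling error at about 8% of patients.** That compares match-first with always entering the non-match (0.090 × 0.875 = 0.079). The second is a bound that an analyst would hardly adopt, because it means knowing the clinical hypothesis and choosing against it.
- **That the missing normal cell is a main fault.** Section 8.2.3 does not propose to drop normal scans, and keeping them in either place gives nearly the same kappa.
- **That the primary result is affected.** The NRI in section 8.2.1 uses the compatibility judgement, not this table.

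**Conclusion.** The point holds. The 8×8 table does not fit the data the protocol collects, and kappa is unique only if no scan carries several of T1–T7, none is normal, and every LUS pattern has a cell.

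Under the assumptions above, a realistic choice between rules moves kappa by 0.03, 0.06 or 0.11 when 5, 10 or 20% of patients are concerned. It matches the confidence-interval half-width at about 16%. The true shares are unknown, and unequal categories would change the values. The normal-scan and focal-pattern gaps are lesser ones.

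The effect is confined to the agreement analysis and its certainty and CT subgroups. It should be corrected before the data are analysed, but it does not threaten the primary analysis.

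**What to change.** Replace the 8×8 table with one 2×2 table for each of T1–T7, with the patient as unit: condition listed among the primary or secondary clinical hypotheses (yes/no) against condition present on LUS (yes/no), with kappa and 95% CI. The SAP should state:

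- **Denominator.** Whether patients whose only hypotheses are secretions or bronchospasm are in the main analysis, with the other choice as a sensitivity analysis. This matters. Take kappa 0.50 at 20% prevalence and let such patients make up 30% of the total. If none has the condition on LUS, kappa becomes (0.888 − 0.7592)/(1 − 0.7592) = 0.53. If 20% of them do, it becomes (0.828 − 0.716)/(1 − 0.716) = 0.39.
- **Normal scans.** Counted as absent for every condition.
- **Inconclusive examinations.** Left out of the 2×2 tables if inconclusive on either side, with their number and cross-classification reported.
- **Mapping.** Which Annexe 4 boxes correspond to each of T1–T7, including the focal interstitial pattern.
- **Certainty subgroups.** Each patient stratified by the certainty of the primary hypothesis.

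If an overall kappa is kept, enter the primary clinical hypothesis, add a normal column on the LUS axis, and choose among several LUS diagnoses by a fixed order that ignores the clinical hypothesis. Match-first should be a sensitivity analysis only.

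**Cost.** SAP wording and minor programming, since the hypotheses and LUS diagnoses are already recorded. There will be several kappas instead of one, an unlisted hypothesis is taken as clinically absent, and the order behind any overall kappa is arbitrary. Rare conditions will be imprecise: at n = 150, kappa 0.5 and equal margins, the SE is 0.207 at 3% prevalence and 0.118 at 10%, so the 95% CI is about ±0.41 and ±0.23.

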 - When the findings from a chest CT-scan less than 12hours old are available;
 - For each clinical hypotheses;
 - For each level of certainty of clinical hypothesis;
 - For type of patients (reasons for admission the most represented);
 - For each research center.
2. Determine the level of agreement between the physiotherapist's diagnosis comparing the clinical vs LUS findings, overall, for the level of certainty of clinical diagnosis and for the population where a CT-scan is available;
3. Determine the frequency of changes in the chest physiotherapy following the assessment of the LUS results, overall and for each type of clinical hypothesis;
4. Determine the frequency of changes in the medical treatment (determined by intensivist) following the assessment of the LUS results performed by the physiotherapist, overall and for each type of clinical hypothesis.

4. Judgement criteria

4.1.Principal judgement criterion

Modification of the clinical decision: agreement (yes/no) between the lung and diaphragm US diagnosis and the clinical diagnosis and modification (yes/no) of the chest physiotherapy protocol, expressed using the Net Reclassification Index (NRI).

4.2.Secondary clinical decision-makingjudgementcriteria

1. Modification of the clinical decision:
 - When a chest CT-scan < 12h is available;
 - For each clinical hypotheses;
 - For the level of certainty of clinical hypotheses (Likert scale: strongly certain, certain, neither certain nor uncertain, uncertain, strongly uncertain);

- For type of patients (reasons for admission the most represented);
 - For each research center.
2. Proportion of agreement between clinical and LUS diagnosis:
- Overall;
 - For the level of certainty of clinical hypotheses (Likert scale: strongly certain, certain, neither certain nor uncertain, uncertain, strongly uncertain);
 - When chest CT-scan < 12h is available.
3. Proportion of cases when the chest physiotherapy protocol is modified following the results of the LUS:
- Overall;
 - For each type of clinical hypothesis;
 - When a chest CT-scan < 12h is available;
4. Modification of the clinical decision of intensivist:
- Overall;
 - For each type of clinical hypothesis;
 - When a chest CT-scan < 12h is available.

5. Inclusion/exclusion criteria:

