6.5.1.4. Clinical hypotheses

Following the examination, he/she will put forward one or several hypotheses concerning the respiratory dysfunction (and not the medical diagnosis) and will either confirm or refute the indications for chest physiotherapy (*cf. annexe 2a*). If chest physiotherapy is indicated, the physiotherapist will specify the protocol to be used. The choice of the treatment modalities with regard to the type of respiratory dysfunction is detailed in annexe 2b.

According to the clinical examination, the clinical physiotherapist formulates one or more of the following clinical hypothesis (*cf annexe 2a*):

- Clinical examination is compatible with retained airway secretions;
- Clinical examination is compatible with bronchospasm;

- Clinical examination is compatible with pneumonia/consolidation;
- Clinical examination is compatible with atelectasis (~~passive or obstructive~~active mechanism);
-
- Clinical examination is compatible with pleural effusion;
- Clinical examination is compatible with pulmonary edema or global interstitial syndrome;
- Clinical examination is compatible with pneumothorax;
- Clinical examination is compatible with reduced aeration at the most dependent parts of the lungs;
- Clinical examination is compatible with unilateral diaphragm dysfunction (~~unilateral or bilateral~~);
- Clinical examination is compatible with bilateral diaphragm dysfunction;
- Clinical examination is inconclusive.

Among the formulated clinical hypotheses, the clinical physiotherapist will choose one primary clinical hypothesis (the choice is left to the discretion of the clinical physiotherapist, based on the probability and priority of the clinical hypothesis in terms of treatment).

A lung and diaphragm US will be done (see below) following the evaluation of the clinical physiotherapist with the physiotherapist who undertakes the US assessment blinded to the clinical assessment findings of the clinical physiotherapist. The clinical physiotherapist will then incorporate the results of the lung and diaphragm US and deem whether they are compatible with the clinical hypotheses put forward. He/she will then specify the chest physiotherapy protocol according to the results of the US-scan.

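### If one primary hypothesis per patient is tabulated, the kappa in section 8.2.3 omits patients labelled retained secretions or bronchospasm, so it is not an overall measure of agreement

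*Combined protocol and SAP*

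**What the plan says.** Section 8.2.3 lists the conditions that enter the kappa, T1 to T7 plus "T8: examination is inconclusive", and prints an 8 × 8 table. It says that diagnoses of retained airway secretions and bronchospasm "aren't included in the analysis as LUS doesn't allow their diagnosis", adding that "LUS may only be compatible with these hypotheses". It then says "The Kappa index will be calculated for the global population", and also for two certainty groups and for patients with a recent CT-scan. The objective served is item 2 of section 3.2, the level of agreement "comparing the clinical vs LUS findings, overall"; section 4.2, item 2, repeats it as a criterion.

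Both omitted diagnoses are permitted clinical hypotheses in section 6.5.1.4: "Clinical examination is compatible with retained airway secretions" and "Clinical examination is compatible with bronchospasm". From the hypotheses formulated, "the clinical physiotherapist will choose one primary clinical hypothesis". Section 7.4.3 has primary and secondary hypotheses recorded in the case report form. Section 6.5.2.3 treats a normal ultrasound profile as compatible with both secretions and bronchospasm.

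**The concern.** That ultrasound cannot diagnose secretions or bronchospasm is a good reason to have no scan category for them. It says nothing about a patient with that clinical label whose scan shows consolidation, effusion or pneumothorax, which ultrasound can detect. In that patient the two methods differ on something both can assess, and the table has nowhere to record it. A patient with that label and a normal scan, a pair the protocol itself calls compatible, has no cell either.

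Entry to the table therefore depends on the clinical rating, which is one of the two ratings compared. The result is an agreement figure for patients given a T1 to T8 clinical label, reported as if it covered everyone. A lesion behind a secretions label is also the kind of discordance this study was set up to find.

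**Working it through.** **Structural check.** Section 8.2.3 defines Pa = Σn_ii/n, Pe = Σ(n_i. × n_.i)/n² and kappa = (Pa − Pe)/(1 − Pe), with sums over T1 to T8. A patient tabulated clinically under secretions or bronchospasm has no row, and so enters none of n, Pa, Pe or kappa. The plan gives no expected kappa or precision for this analysis, so there is no planned figure to reproduce.

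**Illustration 1: one lesion, present or absent.** Only the total of 150 (section 8.1) and the formulas come from the plan. Everything else is assumed. Suppose 90 patients enter and 60 are left out. Among the 90, clinician and scan both report consolidation in 25, the clinician alone in 10, the scan alone in 15, and neither in 40.

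- Pa = (25 + 40)/90 = 0.722
- Pe = (35 × 40 + 55 × 50)/90² = 4150/8100 = 0.512
- kappa = (0.722 − 0.512)/(1 − 0.512) = 0.43

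Now add the 60, all clinically absent for consolidation, with x positive scans. Then Pa = (125 − x)/150 and Pe = [35(40 + x) + 115(110 − x)]/150².

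| x of 60 | Pa | Pe | kappa, all 150 |
|---|---|---|---|
| 0 | 0.833 | 0.624 | 0.56 |
| 15 | 0.733 | 0.571 | 0.38 |
| 30 | 0.633 | 0.518 | 0.24 |
| 45 | 0.533 | 0.464 | 0.13 |

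The all-patient kappa equals the restricted 0.43 at about x = 10. Below that the restricted kappa is too low; above it, too high. Raw agreement turns at a different point. It falls only when x/60 exceeds the disagreement rate elsewhere, 25/90 = 28%. At x = 15 (25%), raw agreement rises from 72.2% to 73.3% while kappa falls from 0.43 to 0.38.

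**Illustration 2: multi-category.** Add a ninth category to the planned table: clinical secretions/bronchospasm against a normal scan. Let s be the share of patients with that clinical label and m the share of those whose scan falls in T1 to T8. Assume T1 to T8 margins of 25, 15, 15, 12, 3, 15, 10 and 5% for both ratings, so the squared shares sum to 0.1578. With 8 × 8 kappa 0.50, its Pa is 0.5 + 0.5 × 0.1578 = 0.579. Then:

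- Pa = (1 − s) × 0.579 + s(1 − m)
- Pe = (1 − s)(1 − s + sm) × 0.1578 + s²(1 − m)

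At s = 30% (45 of 150 patients) and m = 50%: Pa = 0.405 + 0.150 = 0.555, Pe = 0.7 × 0.85 × 0.1578 + 0.045 = 0.139, and kappa = 0.48. The same formulas give:

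| s | m = 0 | m = 50% | m = 80% | m = 100% |
|---|---|---|---|---|
| 10% | 0.56 | 0.50 | 0.47 | 0.44 |
| 30% | 0.65 | 0.48 | 0.39 | 0.33 |
| 50% | 0.70 | 0.44 | 0.31 | 0.23 |

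For s from 10 to 50%, the restricted 0.50 is too high once m passes a point between 0.51 and 0.37. If the 8 × 8 kappa is 0.70, that point lies between 0.31 and 0.20.

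**Comparison with the other analyses.** Under section 8.2.1, a scan incompatible with the clinical diagnosis makes a non-event in the NRI, and no diagnosis is excluded. Section 8.2.4 (proportion modified) states no exclusion either. A patient with secretions and an incompatible scan can therefore count there and be absent from the kappa.

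**The case against.** The strongest reply is that section 8.2.3 leaves out diagnoses, not patients, and openly gives its reason. Secondary hypotheses are recorded, so a patient with secretions and consolidation could enter under T1 if all hypotheses were tabulated. This stands in part. A reader might infer that every patient with either diagnosis is lost, but that follows only if one primary label per patient is used. The plan does not say so; the single-label table merely implies it. Even if all hypotheses were tabulated, patients with secretions or bronchospasm alone would still have no row.

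Nor can every such exclusion be called a lesion the clinician missed. Section 6.5.1.4 has the primary hypothesis chosen on probability and treatment priority, so the lesion may be recorded as secondary. Misses behind other labels, such as clinical T8 with scan T1, do have a cell.

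A reader might also infer that the planned kappa is inflated. The documents do not support a direction: they give neither the share of such patients nor their scan findings, and concordant pairs are dropped too.

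Finally, the primary NRI can count these discordances, so they are not lost to the trial. That is right, and it limits the importance of the point.

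**Conclusion.** The point holds as a defect in a secondary analysis. On the primary-hypothesis reading, the kappa called global, and the overall agreement of objective 2, describe only patients with a T1 to T8 clinical diagnosis. The certainty and CT-scan kappas have the same restriction. The stated reason supports dropping two categories but not ignoring what the scan shows in these patients.

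Direction and size are unknown. Under the assumptions above, counting these patients could move a kappa of 0.43 to anything from 0.56 to 0.13 in the single-lesion example, or a kappa of 0.50 to anything from 0.70 to 0.23 in the nine-category one. These ranges show that the restriction can matter; they do not estimate the error in the planned 8 × 8 kappa. The NRI and the proportion modified are not affected by this rule.

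**What to change.** For the overall agreement objective, keep all patients. For each ultrasound-detectable condition T1 to T7, code present or absent from all recorded clinical hypotheses (primary and secondary), code the scan likewise, and report agreement and kappa with confidence intervals. Secretions or bronchospasm alone counts as absent for T1 to T7. State beforehand how inconclusive examinations and scans are coded, and which entries of the Annexe 4 report correspond to each condition. This also places a clinical T1 to T7 diagnosis with a normal scan: Annexe 4 lists normal and no conclusion separately, but the 8 × 8 table has no normal column.

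Keep the planned 8 × 8 kappa, labelled as restricted to T1 to T8 clinical diagnoses. State its unit of analysis, and report how many patients were left out and what their scans showed.

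The cost is a change to the analysis text and a little more analysis work; the hypotheses and scan diagnoses are already recorded. The drawback is several kappas instead of one, some of them imprecise for rare conditions.
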